## **Background and Review of Literature:**

The long term objective of this project is to validate botulinum toxin injections as a non-inferior treatment option for pain control and ability to return to full activity for adult military members suffering from lower extremity Chronic Exertional Compartment Syndrome (CECS), when compared to surgical fasciotomy. CECS is a debilitating disorder in which pressure in muscle compartments increases with exercise and resolves with rest. This causes pain, paresthesia, and inability to tolerate exercise. CECS mainly afflicts the lower extremities, below the knee, but upper extremity CECS has also been reported. CECS mainly affects young active adults. At risk groups include males, active duty military members, and athletes, both professional and recreational. 1,3,4,5

The current standard for definitive management and treatment of CECS is surgical fasciotomy. According to a 2016 systematic review, surgical intervention for CECS is successful in only 66% of those affected, with 13% of patients reporting complications from surgery, and 6% needing a repeat procedure. Definition of success varied across studies, but included patient satisfaction, lack of surgical revision, and full return to activity. Besides risks and complications, surgery also required a mean of 13 weeks to return to full activity when effective. A 2011 Cohort showed 81% overall patient satisfaction with the procedure, but noted best results from fasciotomy were young participants <23 years old, who underwent isolated anterior compartment release. Satisfaction was defined as being pain free or significantly improved on a 5 point pain scale, varying from pain free to worse. A smaller 2014 retrospective chart review of elite athletes with CECS showed fasciotomy was initially successful in 85% with a mean return to elite activity of 10.4 weeks. However, 30.8 % had a return of symptoms within the follow-up period.

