paresthesia relief from CECS after 1 set of injections for a recreational female athlete. In this report, the patient's symptoms resolved within 1 week. More importantly, she was able to return to full recreational activity within 4 weeks, with no return of symptoms throughout the 14 months of follow up without any weakness or adverse effect. However; current studies regarding dosage and long term recovery are limited. This study aims to further investigate effectiveness of dose dependent botulinum toxin injections to relieve pain and discomfort of CECS, time to return to full activity, long term effects of this intervention, and prevention of surgical fasciotomy.

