For those diagnosed with CECS and desire surgical fasciotomy, the team will discuss the fasciotomy procedure and risks as mentioned above. For the procedure, the patient will be placed under general anesthesia and then linear incisions will be made into the affected compartment releasing the underlying fascial layer, reducing the pressure of the compartment. The entire procedure will be accomplished in a sterile fashion. Further details and scheduling will be per the orthopedic surgeon's recommendations.

After the initial Botulinum toxin injection regimen or fasciotomy, patients will be assessed at 1 month, 3 months, and 6 months with the LEFI and universal pain scale. Primary outcome will be pain reduction. Adequate pain reduction will be rated as less than 3 on the universal pain scale. Secondary outcomes will include return to full activity and patient satisfaction. Full activity is defined as able to run 1.5 miles and complete work duties with either no pain or pain that can be ignored. To assess patient satisfaction, patients will be asked if they were or were not satisfied with the Botulinum toxin injections at the 6 month visit.

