# Categories of subjects: None

## **Clinical Care:**

All subjects will receive standard care for any illness or disease found during the course of this study. At no time will this study preclude them from receiving any treatment for diseases related or unrelated to the study.

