# **Outcome Measures:**

For the prospective portion of the study, the primary outcome will be pain reduction from either a standard of care surgical fasciotomy or an investigational Botulinum toxin treatment regimen. Adequate pain reduction will be rated as less than 3 on the universal pain scale. Secondary outcomes will include return to full activity and patient satisfaction. Full activity is defined as being able to run 1.5 miles and complete work duties with either no pain or pain that can be ignored. To assess patient satisfaction, patients will be asked if they were or were not satisfied with their surgical fasciotomy or their Botulinum toxin injections during their 6 month follow-up visit.

For the retrospective portion of the study, the same measures will be addressed for subjects who have undergone a standard of care surgical fasciotomy, but only on a pre- and post-treatment basis.

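### The plan has no rule for a fasciotomy after injection (or a repeat procedure after fasciotomy), and no outcome measures its stated aim of preventing fasciotomy

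*Combined protocol and SAP*

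**What the plan says.** The last paragraph of the Background and Review of Literature ends its list of what will be investigated with "prevention of surgical fasciotomy". The Significance and Benefits sections likewise present the injection as a way to avoid an operation.

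The Outcome Measures section states that "the primary outcome will be pain reduction from either a standard of care surgical fasciotomy or an investigational Botulinum toxin treatment regimen". The criterion, given there and in section 3a (Interventions and Observations), is: "Adequate pain reduction will be rated as less than 3 on the universal pain scale". It then adds: "Secondary outcomes will include return to full activity and patient satisfaction". The Data Analysis and Statistical Analysis sections add only the LEFI. The procedures table under Source of Research Material lists imaging and blood tests, pressure readings, LEFI, pain scale, satisfaction survey and pregnancy test. It has no entry for a later procedure.

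On timing, section 3a says: "After the initial Botulinum toxin injection regimen or fasciotomy, patients will be assessed at 1 month, 3 months, and 6 months". On further treatment, the Clinical Care section says: "At no time will this study preclude them from receiving any treatment for diseases related or unrelated to the study".

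No section says how a patient who has both treatments, or the same treatment twice, is to be grouped or scored.

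**The concern.** The injection is proposed as a substitute for surgery, and the Objectives ask whether it is non-inferior. An injected patient who gets no relief may go on to the comparator operation within follow-up. Nothing prevents this, and these patients have already failed conservative care and been offered a surgical referral at entry. If the operation works, the 6-month pain score may fall below 3, and on the written criterion the patient can be scored as an injection success. Relief produced by the comparator would then be credited to the treatment meant to replace it. The same applies to return to full activity and satisfaction. A revision after a failed fasciotomy raises the same question in the other arm.

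Separately, data collected as written cannot show how many injected patients avoided surgery, so one of the study's stated aims would go unanswered.

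**Working it through.** **The plan's own figure.** The only calculation in the plan is the power table (67% fasciotomy success against 75% to 95% injection success, two-sided alpha 0.05, power 0.8, equal groups). The pooled-variance formula for two proportions reproduces all five totals: 1008, 360, 176, 98 and 60. The table is correct on its inputs and this point does not change it. It includes no allowance for crossover.

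**Is later surgery captured anywhere?** Comparing the stated aim with the outcome list, the analysis sections and the procedures table shows no item that would record it.

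**Where would an injected, then operated patient be counted?**
- Pointing to the injection group: visits run from the initial treatment, the success criterion has no condition on later treatment, and prior injection in the affected limb bars new entry to the fasciotomy arm.
- Pointing elsewhere: Research Design and Methods and Data Analysis describe the groups by treatment received, so the patient also fits the fasciotomy group.
- No text settles it.

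**Size if counted in the injection group.** Let p be the success rate on injection alone, f the share of injection failures operated on early enough to affect the 6-month score, and s the success rate of that operation.

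Apparent success = p + (1 − p) × f × s, so inflation = (1 − p) × f × s.

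Inputs:
- s = 66%, the systematic-review figure in the Background. The power table uses 67%, which hardly changes the result.
- p = 50% is an assumption. p = 75% is the lowest planning scenario in Data Analysis. p = 94% is the case-series figure in the Background.
- f = 25% to 75% is an assumption. The documents give no crossover rate.

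| p | Inflation, f = 25% | f = 50% | f = 75% | Apparent success, f = 25% to 75% |
|---|---|---|---|---|
| 50% | 0.50 × 0.25 × 0.66 = 8.25 points | 16.5 | 24.75 | 58% to 75% |
| 75% | 0.25 × 0.25 × 0.66 = 4.1 points | 8.3 | 12.4 | 79% to 87% |
| 94% | 0.06 × 0.25 × 0.66 = 1.0 point | 2.0 | 3.0 | 95% to 97% |

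With f = 0 there is no inflation.

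**In patients, at p = 50%.** If all 15 prospective patients are injected: 15 × 0.0825 = 1.2 to 15 × 0.2475 = 3.7, or about 1 to 4. Research Design and Methods describes two arms followed prospectively, so perhaps only 7 or 8 are injected: 7 × 0.0825 = 0.6 to 8 × 0.2475 = 2.0, or about 1 to 2.

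**Timing.** The Purpose of Study section quotes 8 to 13 weeks to full activity after surgery. Six months is about 26 weeks, and 26 − 13 = 13 weeks. So mainly operations in about the first 3 months would improve the 6-month score, which limits how large f can be.

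**The case against.** A reader might infer that the plan counts such a patient as an injection success, so that the injection rate is biased upward. The documents do not support that. They contain no crossover rule, only silence. The patient could be kept under injection, counted under fasciotomy, or dropped. The primary outcome is worded as pain reduction from either treatment, which could even be read as excluding relief from a later operation. This objection stands, and the claim is limited to what the written definition permits. Silence is still not neutral. Dropping operated failures also moves the figure: with p = 50% and f = 50%, 0.50 / (1 − 0.25) = 66.7%. With no rule, the choice would be made after the data are seen.

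Scoring pain regardless of later surgery is a recognised treatment-policy estimand, not an error in itself. That also stands. It has to be chosen and stated, and alone it cannot answer the prevention aim.

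The inputs are soft. The 50% success and the crossover shares are assumed, and the plan's own injection figures (75% to 95%) give much smaller effects. The 66% mixes several definitions of success, none of them pain below 3, and is applied here to injection failures. With the 47% symptom improvement quoted from a United Kingdom military study, the middle case is 0.50 + 0.25 × 0.47 = about 62%. The review figures of "13% of patients reporting complications from surgery, and 6% needing a repeat procedure" carry no time window, so they do not show repeat surgery within 6 months. No primary time point is named among 1, 3 and 6 months.

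Finally, the prevention aim is in one closing Background sentence and not in the Objectives, and this is a small pilot. That lowers the stakes, but the remedy is cheap and the omission would carry into any larger study.

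**Conclusion.** The point holds in limited form. No outcome measures the stated aim of preventing fasciotomy; this follows directly from the text. The plan also has no rule for a second procedure, so on the written definition an injected patient who is later operated on can count as an injection success.

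The documents do not establish that this will happen, or how often. The size is illustrative: 8 to 25 points with p = 50%, 4 to 12 with p = 75%, 1 to 3 with p = 94%, and none without crossover. These figures assume that the patient stays in the injection group, that 25% to 75% of failures are operated on in time, that 66% surgical success applies to them, and that 6 months is the time point. The plan should be changed on this point, but its power table is not in question.

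**What to change.** 1. Record any second procedure on the study limb and compartment (fasciotomy, repeat fasciotomy, repeat injection), with its date, at the 1, 3 and 6 month contacts. For the retrospective fasciotomy group, obtain the same from the records and the survey over the same 6-month window, so that both groups are held to one standard.
2. Add a secondary outcome: free of fasciotomy (injection arm) or of a repeat procedure (fasciotomy arm) at 6 months, with an exact 95% confidence interval.
3. Fix the analysis group by initial treatment, and name 6 months as the time point for the success proportion.
4. Report success as pain below 3 without a second procedure. Alongside it, as a sensitivity analysis, report pain below 3 regardless of later treatment.

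The cost is one question at existing contacts, a short addition to the outcome definition, and possibly a less favourable success proportion. Clinical care does not change.

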### 3. RESEARCH DESIGN AND METHODS

## **Research Design and Methods:**

The study will be a prospective cohort pilot study designed to compare Active Duty patients, 18 years of age or older, with CECS undergoing two different treatment interventions. The first arm will be patients receiving investigational botulinum toxin injections. The second arm will be patients who undergo the standard of care surgical fasciotomy. Both arms will be evaluated for pain relief with the universal pain scale and lower extremity functional index (LEFI) surveys at pre-treatment and again at one, three, and six months post-treatment. At the six month follow up, subjects will be asked the Satisfaction Survey (in-person, via Survey Monkey or Google Forms). Clinical data that will be analyzed for research purposes in both groups include age, sex, height, weight, body mass index, time to diagnosis, minutes of exercise prior to onset of symptoms, minutes of rest before relief of symptoms, LEFI and pain on the Universal Pain Assessment Tool.

In addition, we will be conducting a retrospective review from July 1, 2016 through June 30, 2017 of patients who have been diagnosed with CECS and have undergone surgical fasciotomy. They will be asked to recall their symptoms both before and six months after their surgery, in order to complete the LEFI and Universal Pain Assessment Tool (in-person, via Survey Monkey or Google Forms). They will also be asked if they were satisfied with their treatment. A HIPAA Waiver Request will be used to access medical records and contact these individuals, followed by each subject being verbally consented to participate in the study prior to completing the LEFI and universal pain scale surveys (in-person, via Survey Monkey or Google Forms). If the subjects refuse to be consented, then no data will be gathered from the subjects or their medical records.

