#### a. Interventions and Observations:

If CECS is diagnosed by intramuscular pressure (IMP) elevation, patients will be offered Botulinum toxin injection regimen into the affected compartment or referral to orthopedic surgeon for a possible surgical fasciotomy. Patients will be provided information regarding both Botulinum toxin injections and fasciotomy. Patients will be allowed to discuss fasciotomy with a surgeon prior to making a decision to participate in the study, if desired. Potential side effects of Botulinum toxin injection include possible bleeding, pain, infection, general muscle weakness, muscular atrophy, flu-like symptoms, breathing and swallowing difficulties and death. Potential side effects of fasciotomy include surgical site pain, bleeding, recurrence of symptoms, scarring, muscle weakness, nerve damage, hematoma, need for repeat operation, infection, reactions to anesthesia (e.g. anaphylaxis), blood clot, muscle wasting (atrophy), and death. These will be explained to participants during the consent discussion.

For those diagnosed with CECS and desire Botulinum toxin injections, they will receive 2 injections per affected compartment. Up to 50 units of Botulinum toxin will be injected into the proximal and distal portions of the compartment for a maximum total dose of 100 units. A solution of 100 units of Botulinum toxin per 2 mL of normal saline will be used for all injections. Standard sterile technique will be followed. Insertion in to the correct compartment will be accomplished using general landmarks. The compartment will be separated into thirds measuring from the tibial plateau to the head of the calcaneus. Injections will be given at approximately 1/3 the distance from the tibial plateau for the proximal injection and 2/3 the distance from the tibial plateau for the distal injection. If the lateral or deep posterior compartment is affected, a total of 50 units Botulinum toxin will be given, 25 units per injection. If the anterior or superficial posterior compartment is affected, a total of 100 units Botulinum toxin will be given, 50 units per injection. Of note, CECS mainly affects the anterior and lateral compartments and is rarely seen in the superficial posterior or deep posterior areas.

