### 6. DATA ANALYSIS

## **Data Analysis:**

Head-to-head comparison of patients undergoing or who have undergone standard of care surgical fasciotomy and investigational Botulinum toxin injections will be analyzed. Measures addressed will be pain severity, return to full activity, Lower Extremity Function index, and patient satisfaction over the course of pre-treatment, post-treatment, and 1, 3, 6 month follow-up visits.

A power analysis, shown below, was completed for this pilot study. Assuming equal sample sizes of groups, 2-tail alpha of .05, power=.8, and 67% of fasciotomy group will have no pain (i.e. pain < 3).4

- 1. 75% of injection group, no pain n=1008 total
- 2. 80% of injection group, no pain n=360 total
- 3. 85% of injection group, no pain n=176 total
- 4. 90% of injection group, no pain n=98 total
- 5. 95% of injection group, no pain n=60 total

As CECS is an infrequent diagnosis, this pilot study will have difficulty over the course of the year to obtain enough sample size for statistical significance. However, the hope is to obtain a promising trend and eventually expand the study to obtain significance pending initial results.

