## **Sample Size Estimation/Power Analysis:**

The expected sample size for the prospective portion of the study is 15. The expected sample size for the retrospective review is 10.

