### **Statistical Analysis:**

The primary measure to be analyzed will be comparing pre- and post-treatment pain for each of the two treatment regimens using the universal pain scale. Additionally, participants will be evaluated for return to duty, overall patient satisfaction, and the Lower Extremity Functional Index will be compared pre- and post-treatment. The study team will complete the statistical analysis.

Number of Subjects:				
	# Planned to Enroll	# Enrolled	# Planned to Complete Study	TOTAL

Number of Subjects at Scott AFB	15	0	15	15
---------------------------------	----	---	----	----

Number of Data Records Entered into the Study:					
	# Planned to Enroll	# Enrolled	# Planned to Complete Study	TOTAL	
Number of Subjects at Scott AFB	10	0	10	10	

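### Only the retrospective fasciotomy patients are scored by recall, and nothing in the plan separates recalled from prospectively measured scores in the comparison with injection

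*Combined protocol and SAP*

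**What the plan says.** Section 3 (Research Design and Methods) describes two prospective arms, injection and fasciotomy. Both are scored for pain and LEFI before treatment and at one, three and six months. It then adds a retrospective group, all with past fasciotomy: "They will be asked to recall their symptoms both before and six months after their surgery".

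Section 6 uses these data as follows.

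- Data Analysis: "Head-to-head comparison of patients undergoing or who have undergone standard of care surgical fasciotomy and investigational Botulinum toxin injections will be analyzed". Its power analysis compares the two treatments on the share with low pain, assuming that "67% of fasciotomy group will have no pain (i.e. pain < 3").
- Statistical Analysis: the primary measure is "comparing pre- and post-treatment pain for each of the two treatment regimens".
- Outcome Measures: the retrospective patients contribute the same measures, "but only on a pre- and post-treatment basis".
- Sample Size Estimation/Power Analysis: "The expected sample size for the prospective portion of the study is 15", and "The expected sample size for the retrospective review is 10". The split of the 15 between injection and surgery is not given.

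Treatment is not randomised. Section 3a says that "patients will be offered Botulinum toxin injection regimen into the affected compartment or referral to orthopedic surgeon for a possible surgical fasciotomy".

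**The concern.** Recall occurs on one side of the comparison only. The fasciotomy side may mix scores taken at the time with scores remembered later, while the injection side has no remembered scores. A difference between treatments could therefore partly be a difference in how pain was measured. The problem concerns the pre-treatment and six-month scores, because recalled patients have no one-month or three-month scores.

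A confidence interval does not show this error, and enlarging the study would not remove it while the recalled share persists. That matters because the Data Analysis section hopes that the pilot will give an encouraging signal on which to expand.

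**Working it through.** **1. The plan's own figures.** The power table sets the scale of effect that the plan has in mind. The formula is n per group = [1.960·√(2p̄q̄) + 0.842·√(p₁q₁ + p₂q₂)]² / (p₂ − p₁)², with p₁ = 0.67, two-sided alpha 0.05, power 0.80, pooled variance and no continuity correction. For p₂ = 0.75:

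(1.960·√0.4118 + 0.842·√0.4086)² / 0.08² ≈ 3.225 / 0.0064 ≈ 503.8, so 504 per group and 1008 in total.

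The same formula gives 360, 176, 98 and 60 for 80%, 85%, 90% and 95%. All five totals match the plan. The gaps sought run from 75 − 67 = 8 points to 95 − 67 = 28 points.

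**2. Recalled share of the fasciotomy group.** Let f be the number of prospective fasciotomies among the 15. It is not stated, so the range is shown; f can be at most 14 if there is to be an injection group. If the sources are pooled, the recalled share is 10/(10+f). In the injection group it is 0% at every f.

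**3. Bias in the share with pain below 3.** Only error in the six-month score matters here. Bias = recall shift × 10/(10+f). The shifts are assumptions.

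| f | Recalled share | 10-point shift | 20-point shift | 30-point shift |
|---|---|---|---|---|
| 0 | 100% | 10 | 20 | 30 |
| 5 | 66.7% | 6.7 | 13.3 | 20 |
| 10 | 50% | 5 | 10 | 15 |
| 14 | 41.7% | 4.2 | 8.3 | 12.5 |

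**4. Bias in the pre/post change.** Let d₀ and d₆ be the mean recall errors before surgery and at six months. Bias = (d₆ − d₀) × 10/(10+f).

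- An assumed 1-point error at both times gives (1 − 1) × share = 0, floor and ceiling effects of the scale aside.
- An assumed 1-point difference between the two errors gives 1.0, 0.67, 0.50 or 0.42 points at f = 0, 5, 10 or 14.
- If a recorded baseline replaced the recalled one, d₀ would be 0 and the common 1-point error would no longer cancel: each such patient would carry a bias of d₆ = 1 point.

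**5. Is f = 0 possible?** Section 3c (Date(s)) describes the prospective portion in terms of injection patients only. Research Design and Methods, section 3a and Outcome Measures all include prospective surgery. The documents do not settle it.

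**6. Do the cohorts overlap in time?** By section 3c, prospective data collection starts in April 2017 and the retrospective surgery window runs to June 30, 2017. A patient operated on between April and June 2017 could qualify for both.

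**7. Cost in precision of leaving out recalled patients.** The 95% half-width is t × SD × √(1/n₁ + 1/n₂), with an assumed SD of 2.5 points. At f = 7:

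- Prospective only, 8 versus 7, 13 df: 2.160 × 2.5 × √(1/8 + 1/7) = 2.8.
- With recalled patients, 8 versus 17, 23 df: 2.069 × 2.5 × √(1/8 + 1/17) = 2.2.

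The corresponding pairs are 3.5 and 2.1 at f = 3, 3.0 and 2.1 at f = 5, and 3.0 and 2.6 at f = 10.

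**The case against.** The strongest reply is that the plan does not say it will pool. Outcome Measures describes the retrospective measures apart, and the subject tables count 15 subjects and 10 records apart. The primary measure is a change within each regimen, with no between-treatment test named. The use of recall is disclosed, and the plan concedes that it will struggle to reach significance. This limits the consequence, but describing and counting cohorts separately is not an analysis rule, and the head-to-head sentence names past fasciotomy patients.

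It is also fair that the size rests on assumptions: the documents give no recall error, SD or split. Nor would separation measure the error well. At an SD of 2.5, recalled versus prospective fasciotomy has a half-width of 3.6, 3.0, 2.6 or 2.3 points at f = 3, 5, 7 or 10. That contrast also mixes in calendar period and who could be reached.

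A reader might infer more than the documents support:

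- *That pooling is planned.* It is the natural reading, but it is not explicit.
- *That measurement mode and treatment are completely confounded.* This follows only if f = 0, and several sections include prospective surgery.
- *That recall favours injection.* Nothing in the documents gives a direction.
- *That the false-positive rate is inflated by a known amount.* No between-treatment test is specified, so no rate can be computed.
- *That recorded baselines should replace recalled ones.* Step 4 shows that this gives up the cancellation of common error, and whether the error is common or differential is unknown.

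**Conclusion.** The point holds as a gap in the analysis plan. Recalled scores come only from fasciotomy patients, those patients enter the comparison with injection, and no section separates the sources there. Measurement mode is partly confounded with treatment, and completely so at f = 0, which remains a live reading.

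If the sources are pooled, between 42% (f = 14) and 100% (f = 0) of any recall shift passes into the share with pain below 3. Under assumed shifts of 10 to 30 points the bias is about 4 to 30 points, comparable with the 8 to 28 points in the power table. The change score is safer, because recall error common to both times cancels.

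The gap is certain from the text; the size is illustrative. The plan should be changed, but the pilot need not stop for it.

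**What to change.** **Section 6, Data Analysis and Statistical Analysis.** Add: *Fasciotomy results are reported separately for prospectively measured patients and for patients with recalled scores. Any fasciotomy-versus-injection comparison is shown with and without the recalled patients. If no fasciotomy patient is enrolled prospectively, it is labelled an exploratory comparison with recalled controls. All versions are non-randomised, because patients choose their treatment.*

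**Section 3c and Sample Size Estimation/Power Analysis.** State the expected split of the 15 between injection and surgery. State that each patient counts in one cohort only, because the two time windows overlap.

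**Research Design and Methods.** Keep the recalled baseline for the change score. Section 3c already plans to review pain assessments, so where a record holds a pre-surgery pain score, show it beside the recalled one as a check on recall only.

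**Cost.** Some wording, a few more rows of results and a look-up in records already under review; no data are discarded. The prospective-only interval is wider (2.8 versus 2.2 points at f = 7, assumed SD 2.5), and at f = 0 there is no prospective-only contrast. Separation discloses the recall problem. With these numbers it cannot measure recall error precisely, and it does not remove confounding by treatment choice.
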